Ref#: INU/REHAB/XC45

Date: 12/05/2026

1. Protocol Summary

Study Type: Observational (Retrospective) **Design:** Single-center, retrospective cohort study

Objective: To evaluate the cognitive effectiveness of combined somatotherapy and occupational therapy in post-stroke patients using Montreal Cognitive Assessment (MoCA) scores.

Enrollment: 50 participants **Study Period:** Data from patients treated between 2018–2019

2. Background and Rationale

Stroke is a major cause of cognitive impairment worldwide. Cognitive deficits significantly affect functional independence and quality of life. Somatotherapy (structured sensorimotor therapy) combined with occupational therapy (task-oriented ADL training) is commonly used in stroke rehabilitation. This retrospective study aims to assess the cognitive benefits of this combined approach.

3. Objectives

[figure not shown]
Primary Objective: To determine the change in cognitive function (measured by MoCA total score) before and after 4 weeks of combined somatotherapy and occupational therapy.

Secondary Objectives:

- To evaluate changes in individual MoCA cognitive domains.
- To determine the proportion of patients achieving MoCA score ≥ 26 after intervention.

4. Study Design

- Retrospective observational study
- Single arm (no control group)
- Data collected from medical records of King Hospital, Swat, Pakistan (2018–2019)

5. Study Population

Swat Campus

Inclusion Criteria:

- Adults (≥ 30 years) diagnosed with ischemic or hemorrhagic stroke (first or recurrent)
- Referred for cognitive rehabilitation
- Received at least 4 weeks of somatotherapy + occupational therapy
- Had pre- and post-therapy MoCA assessment

Exclusion Criteria:

- Severe aphasia or speech impairment preventing MoCA testing
 - Significant visual or hearing impairment interfering with testing
 - Incomplete medical records
-

6. Intervention / Exposure

Combined Somatotherapy and Occupational Therapy

- Duration: 4 weeks
 - Frequency: 5 sessions per week
 - Session length: 35 minutes
 - Somatotherapy: Sensorimotor training, balance, coordination, and movement therapy
 - Occupational Therapy: Patient-specific ADL training with cognitive integration
 - Equipment: Adjustable tables/chairs, wheelchairs, splints, and assistive devices
-

7. Outcome Measures

Primary Outcome: Change in MoCA Total Score (0–30) from baseline to 4 weeks.

Secondary Outcomes:

- Changes in MoCA subdomain scores (Visuospatial/Executive, Naming, Attention, Language, Abstraction, Delayed Recall, Orientation)
 - Percentage of patients with MoCA ≥ 26 (normal range)
-

8. Statistical Analysis Plan (SAP)

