8.3 Inferential Statistics

- **Primary Analysis:** Wilcoxon Signed-Rank Test to compare pre- and post-intervention MoCA total scores (non-parametric test for paired data).
- **Secondary Analysis:**
 - Spearman Rank Correlation between baseline and final MoCA scores.
 - Wilcoxon Signed-Rank Test for individual MoCA domains.
 - McNemar's test for proportion of patients with MoCA ≥ 26 before vs after intervention.

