8.4 Subgroup Analysis (Exploratory)

- By age, gender, and stroke type (ischemic vs hemorrhagic), if sample size permits.

8.5 Significance Results will be considered statistically significant at $p < 0.05$.

9. Data Management and Ethics

- Data were collected retrospectively from hospital records.
- Patient confidentiality and privacy maintained (anonymized data).
- No individual patient data will be shared publicly.

Ethical Considerations: This study was conducted in accordance with the Declaration of Helsinki. Being retrospective, it was exempted from informed consent requirement by the hospital administration.

Approval: This protocol has been prepared for registration on ClinicalTrials.gov

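### Sections 1 and 2 promise effectiveness and benefit, but a single-arm pre/post test against zero change can only show that MoCA scores changed

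*Combined protocol and SAP*

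**What the plan says.** The aim appears in three places, in two different senses.

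- Section 1 (Protocol Summary), Objective: "To evaluate the cognitive effectiveness of combined somatotherapy and occupational therapy in post-stroke patients using Montreal Cognitive Assessment (MoCA) scores".
- Section 2 (Background and Rationale): "This retrospective study aims to assess the cognitive benefits of this combined approach".
- Section 3, Primary Objective: "To determine the change in cognitive function (measured by MoCA total score) before and after 4 weeks" of the combined therapy.

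The first two ask what the therapy does. The third asks how scores moved.

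Section 4 describes the design as "Single arm (no control group"). Section 1 gives the size: "Enrollment: 50 participants". The primary analysis in Section 8.3 is "Wilcoxon Signed-Rank Test to compare pre- and post-intervention MoCA total scores (non-parametric test for paired data"). Sections 8.1 and 8.5 set the threshold at 0.05, two-tailed in 8.1. Section 8.5 says only "Results will be considered statistically significant at" that level and does not say what a significant result will be taken to mean.

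The other analyses in 8.3 are a Spearman correlation of baseline with final MoCA, Wilcoxon tests by domain, and McNemar's test for MoCA of 26 or more before versus after. The document has no comparator, external benchmark, expected-recovery value or statement of limitations.

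**The concern.** Effectiveness is a contrast between what happened with the therapy and what would have happened without it. The plan observes only the first. Testing against zero stands in for the second only if untreated patients would on average show no change over the same interval, and the plan neither says nor defends that.

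Several features of the plan leave room for a non-zero change without any therapy effect:

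- The eligibility criteria set no limit on time since stroke, so natural recovery is not excluded.
- The same scale is given twice about 4 weeks apart, with no stated measure against practice effects.
- Entry is by referral for cognitive rehabilitation, which makes regression to the mean possible.
- Only patients with at least 4 weeks of therapy and both scores are included, so those who stopped early are absent.

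The secondary analyses do not help. The domain Wilcoxon tests and McNemar's test are also pre/post comparisons with a null of no change, and a baseline-to-final correlation does not measure benefit. If a significant result were reported under the Section 1 objective, readers would take it as evidence that the therapy works, which the data cannot show.

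**Working it through.** The plan gives no power calculation, target effect or SD, so there is no figure of its own to reproduce. The check asks how often a therapy with no effect would still produce a significant improvement.

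**Inputs from the document:** n = 50 (Section 1); two-sided alpha 0.05 (8.1); paired Wilcoxon signed-rank test with a null of no change (8.3).

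**Assumed inputs, not in the document:** SD of MoCA change 2 to 5 points; mean non-therapy change (drift) 0 to 3 points; roughly normal change scores.

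**Formula.** With asymptotic relative efficiency 3/π for the signed-rank test under normality,

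P(significant improvement) ≈ Φ( (drift/SD) × √(50 × 3/π) − 1.960 ), where √(50 × 3/π) = √47.75 = 6.910.

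**Worked cells**

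- Drift 1, SD 3: 6.910/3 − 1.960 = 0.343, and Φ = 0.63.
- Drift 0.5, SD 2: 0.25 × 6.910 − 1.960 = −0.232, and Φ = 0.41.
- Drift 0.5, SD 5: 0.10 × 6.910 − 1.960 = −1.269, and Φ = 0.10.

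**Full grid**

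| SD of change | drift 0 | 0.5 | 1 | 1.5 | 2 | 3 |
|---|---|---|---|---|---|---|
| 2 | 0.025 | 0.41 | 0.93 | 0.999 | >0.999 | >0.999 |
| 3 | 0.025 | 0.21 | 0.63 | 0.93 | 0.996 | >0.999 |
| 4 | 0.025 | 0.14 | 0.41 | 0.74 | 0.93 | 0.999 |
| 5 | 0.025 | 0.10 | 0.28 | 0.55 | 0.79 | 0.99 |

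A simulation of the signed-rank test on integer-rounded changes (2,000 runs per cell, zeros dropped, variance corrected for ties) agrees within about 0.03. A noncentral-t calculation for the paired t-test agrees more closely still.

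**Drift needed for a given probability.** Solving the formula gives drift/SD = (1.960 + z)/6.910. For 80%, (1.960 + 0.842)/6.910 = 0.405. For 50%, 1.960/6.910 = 0.284. In MoCA points, the 80% threshold is 0.405 × SD: about 0.8, 1.2, 1.6 and 2.0 points for SD 2, 3, 4 and 5.

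**The case against.** The strongest reply is that the formal primary objective in Section 3 and the primary outcome in Section 7 ask only for the change in MoCA, and the Wilcoxon test answers that. The single-arm retrospective design is openly stated. This stands, and it confines the problem to the Section 1 objective and the Section 2 aim. It does not remove the problem, because Section 1 is the headline objective, and disclosing a single arm does not make an effectiveness question answerable.

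Three stronger readings are tempting but not supported by the document.

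- A reader might infer that an inert therapy would very probably be declared effective. The probability depends on drift and SD, which the plan does not give. Over the assumed ranges it runs from 0.025 to nearly 1.
- A reader might infer that p < 0.05 is the plan's rule for declaring effectiveness. Section 8.5 speaks only of statistical significance, and no section links it to a conclusion about the therapy.
- A reader might infer that patients were referred because they scored low, so that regression to the mean is certain. The criterion is referral for cognitive rehabilitation, with no MoCA entry threshold. McNemar's test of 26 or more before versus after allows for patients already at that level at baseline. Natural recovery cannot be sized either, since time since stroke is not given.

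**Conclusion.** The concern holds as a mismatch between aim and analysis. The causal aim in Sections 1 and 2 cannot be answered by a one-arm test against zero change, whatever the drift turns out to be, and it conflicts with the descriptive objective in Section 3. The Section 3 objective itself is answerable as planned.

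The size of the risk is conditional. With 50 patients, no therapy effect and the assumed SDs of 2 to 5 points, a significant improvement is at least 80% likely only if non-therapy drift is about 0.4 SD or more. For a 0.5-point drift it is well below that. These figures illustrate how sensitive the test is to drift. They do not estimate what happened in this cohort.

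**What to change.** 1. In Sections 1 and 2, replace the effectiveness and benefit wording with: *describe the within-patient change in MoCA total score over 4 weeks of combined therapy*. Section 3 already says this in substance and needs no change.
2. Add to 8.5: *p < 0.05 shows only that scores changed; no claim that the therapy caused the change will be made from it.*
3. In 8.3, report the change in MoCA total with a 95% confidence interval. A Hodges–Lehmann estimate and interval would sit naturally with the signed-rank test. Optionally, note the largest non-therapy gain the interval excludes, which is its lower limit. This helps a reader judge drift, but it does not settle attribution unless a drift value can be justified.

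The cost is a few lines of text and one interval, with no new patients or data. The document says it was prepared for registration, so the wording can be aligned there too. The downside is a weaker headline claim.

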8.1 General Principles

- Software: SPSS version 23.0
- Significance level: $p < 0.05$ (two-tailed)
- Handling of missing data: Complete case analysis (only patients with both pre and post MoCA scores included)

8.2 Descriptive Statistics

- Continuous variables: Mean \pm SD or Median (IQR) as appropriate
- Categorical variables: Frequency and percentages

8.3 Inferential Statistics

- **Primary Analysis:** Wilcoxon Signed-Rank Test to compare pre- and post-intervention MoCA total scores (non-parametric test for paired data).
- **Secondary Analysis:**
 - Spearman Rank Correlation between baseline and final MoCA scores.
 - Wilcoxon Signed-Rank Test for individual MoCA domains.
 - McNemar's test for proportion of patients with MoCA ≥ 26 before vs after intervention.

8.4 Subgroup Analysis (Exploratory)

- By age, gender, and stroke type (ischemic vs hemorrhagic), if sample size permits.

8.5 Significance Results will be considered statistically significant at $p < 0.05$.

9. Data Management and Ethics

- Data were collected retrospectively from hospital records.
- Patient confidentiality and privacy maintained (anonymized data).
- No individual patient data will be shared publicly.

Ethical Considerations: This study was conducted in accordance with the Declaration of Helsinki. Being retrospective, it was exempted from informed consent requirement by the hospital administration.

Approval: This protocol has been prepared for registration on ClinicalTrials.gov

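### Section 8.4 plans an age subgroup with no cut stated; analysing age as a continuous variable would keep information that grouping throws away

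*Combined protocol and SAP*

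**What the plan says.** The subgroup provision is a single line under a heading that marks it as exploratory: analyses are planned "By age, gender, and stroke type", conditional on sample size. Stroke type has its two levels written out and gender is categorical by nature. For age there is no cut, no number of groups and no test. Section 8.4 also does not say what sample size would permit the analysis. Nothing in sections 8.2 to 8.5 plans age as a continuous term.

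Four other places bear on this:

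- Section 5 sets a lower age limit of 30 years and no upper limit. The documents give no age distribution.
- Section 1 gives the enrollment as "50 participants", and section 4 describes the design as "Single arm (no control group"). An age analysis can therefore only relate age to pre-post change, or to the final score given baseline.
- Section 1 places treatment in 2018–2019, the document is dated 12/05/2026, and section 9 states: "Data were collected retrospectively from hospital records".
- Section 8.5, directly after the subgroup line, applies one unadjusted 5% threshold and makes no exception for subgroups.

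**The concern.** Two separate matters arise.

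The first is efficiency. Splitting patients into younger and older treats everyone on one side of the cut as the same age. With 50 patients there is little information to spare, and the plan's own caveat about sample size concedes as much. A real age gradient could be missed because of the method.

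The second is an open analytic choice. In a prospective study a late cut can still be fixed before outcomes exist. Here both MoCA scores were recorded years before the plan was dated, so only a written rule would show that the cut was not picked for its result. The plan has no such rule.

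What is at stake is the age result alone.

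**Working it through.** **The plan's own figure.** The enrollment of 50 cannot be reproduced, because the documents give no effect size, SD or power. No figure is stated for the age subgroup.

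**Inputs.** From the documents: n = 50 (section 1), one arm (section 4), two-sided 5% level (section 8.1). Assumed, because the documents are silent: the age distribution (normal or uniform), a linear relation of age to MoCA change, a correlation of 0.3 or 0.4, and the test used to compare age groups.

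**Step 1: information kept by a median split.** Under a linear relation, the share kept is the squared correlation between age and the younger/older indicator.

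- Normal age: correlation √(2/π) = 0.798; squared, 2/π = 0.64. Then 50 × 0.637 = 31.8, so 50 patients act like about 32. Loss: 36%.
- Uniform age: correlation √3/2 = 0.866; squared, 0.75. Then 50 × 0.75 = 37.5. Loss: 25%.

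**Step 2: power by formula.** By Fisher's transformation, power ≈ Φ(atanh(r) × √(n − 3) − 1.96), with √47 = 6.856. For a median split of normal age, r is replaced by 0.798 r.

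- r = 0.3, continuous: 0.3095 × 6.856 = 2.122; Φ(0.162) = 56%.
- r = 0.3, split (r becomes 0.239): 0.2441 × 6.856 = 1.673; Φ(−0.287) = 39%.
- r = 0.4, continuous: 0.4236 × 6.856 = 2.904; Φ(0.944) = 83%.
- r = 0.4, split (r becomes 0.319): 0.3307 × 6.856 = 2.267; Φ(0.307) = 62%.

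**Step 3: power by simulation** (normal age; 10,000 data sets per setting for the first two rows).

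| Comparison | r = 0.3 | r = 0.4 |
|---|---|---|
| Pearson, continuous age / t test at median split | 57% / 39% | 84% / 63% |
| Spearman, continuous age / rank-sum at median split | 53% / 37% | 79% / 61% |
| Linear model adjusted for baseline MoCA / median split | 55% / 38% | 83% / 62% |

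With no true age relation, both continuous tests reject in 5.0% of data sets. A 30/70 split does worse than the median split (rank-sum power 34% at r = 0.3).

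**Step 4: false age findings** (40,000 data sets with no age effect; rank-sum test of MoCA change between age groups, nominal 5%).

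| How the cut is chosen | False-positive rate |
|---|---|
| One median cut, set without regard to outcome | 5.0% |
| Best of 3 cuts (about the quartiles and the median) | 12% |
| Best of 5 central cuts | 14% |
| Best of all cuts from the 20th to the 80th percentile | 28% |
| Best of all cuts from the 10th to the 90th percentile | 37% |

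The rate rises only when a cut is selected by its result. A cut fixed late, but without regard to outcome, costs nothing in error rate.

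**The case against.** A reader might infer that section 8.4 forces a cut, and that any cut made once the outcomes are on file pushes the error rate above 5%. The documents support neither inference. The section names no groups and no test, so a continuous analysis is not excluded; grouping is only its natural reading. Step 4 shows that inflation comes from selection among cuts, not from timing. The documents do not say that several cuts will be tried, that the best will be reported, or that anyone has looked at outcomes by age.

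The between-group rank test is also this review's assumption. The SAP's only test of change in MoCA total is the within-patient signed-rank test in section 8.3. A subgroup analysis might simply repeat that test within each age group, and the rates in step 4 would not describe that.

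Three further points are fair. The correlations of 0.3 and 0.4 and the linear relation have no source in the documents. A linear model departs from the plan's rank-based methods and has to cope with a scale bounded at 0 and 30. And the analysis is exploratory, conditional on sample size, and outside the primary and secondary analyses.

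These points limit the weight of the concern without removing it. The loss of information in step 1 occurs with entirely proper conduct, and an exploratory label does not recover it. The bounded scale is a reason to offer a rank-based option, and the Spearman row in step 3 shows that its advantage over a split is similar.

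**Conclusion.** The point holds as a minor improvement. On its natural reading, section 8.4 groups a continuous variable at an unstated cut. If age and change are roughly linearly related, a median split discards about 25% to 36% of the information, which in a study of 50 means some 16 to 21 percentage points of power at the assumed correlations. That conclusion does not depend on how the cut is chosen. If the relation is far from linear or monotone, these figures do not apply.

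The false-positive rate of 12–37% is conditional: it applies only if several cuts are tried, the best is reported, and a between-group rank test is used. It is a risk that the plan leaves open, not a property of the plan as written.

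**What to change.** In section 8.4, replace the age subgroup with age in years as a continuous variable, and name one of two analyses:

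- a linear model of post-therapy MoCA on baseline MoCA and age, reported as MoCA points per 10 years with a 95% CI; or
- in keeping with the rank-based methods in section 8.3, the Spearman correlation of age with MoCA change.

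If age groups are wanted for a table, split at the cohort median and give descriptive figures without a test.

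The cost is one sentence of SAP text and no new data. The linear model assumes a roughly linear relation and tolerable ceiling effects on the 0–30 scale; Spearman assumes a monotone relation. A scatterplot of change against age can check both.

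### Section 8.5 lets each of the seven MoCA domain tests and the MoCA ≥ 26 test be declared significant at 0.05 with no multiplicity control, and only the subgroups are labelled exploratory

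*Combined protocol and SAP*

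**What the plan says.** Section 8.1 sets a two-sided 0.05 level as a general principle. Section 8.5 repeats the threshold without limiting it to any analysis: "Results will be considered statistically significant at" p < 0.05.

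Section 8.3 names one primary analysis, the paired Wilcoxon test on the MoCA total. Its secondary list has three entries:

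- "Wilcoxon Signed-Rank Test for individual MoCA domains"
- "McNemar's test for proportion of patients with MoCA ≥ 26 before vs after intervention"
- "Spearman Rank Correlation between baseline and final MoCA scores"

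Section 7 shows how many domains are meant: "Changes in MoCA subdomain scores (Visuospatial/Executive, Naming, Attention, Language, Abstraction, Delayed Recall, Orientation". That is seven. Domain changes and the proportion reaching 26 are also the two secondary objectives in section 3.

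The exploratory label appears only in the heading of section 8.4, on subgroups. The document gives no multiplicity adjustment, no order of testing, no condition that the primary test must succeed first, and no statement that secondary p-values are descriptive.

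**The concern.** As written, any one of eight secondary tests that crosses 0.05 can be reported as statistically significant, with the same standing as the primary result. The nominal 5% then describes each test on its own, not the set of secondary claims.

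What is at stake is which single-domain statements the report may make. A statement that, say, naming or delayed recall changed significantly would rest on a rule under which a chance finding somewhere in the set is considerably more likely than 5% when nothing has changed. The conclusion on the MoCA total is not at stake.

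**Working it through.** **Inputs from the document.** Level 0.05 two-sided per test (8.1, 8.5); seven domain tests (7, 8.3); one McNemar test (8.3), making eight; 50 patients (1). The Spearman correlation would be a ninth secondary test but is not a test of change, so it is left out of the family. The plan states no family-wise error rate, so there is no figure of its own to reproduce.

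**Input assumed.** The correlation between the test statistics is not given. A range is shown.

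**Step 1: independent tests, no true change.** The chance of at least one p < 0.05 among k tests is 1 − 0.95^k.

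- k = 7: 1 − 0.95^7 = 1 − 0.698 = 30.2%
- k = 8: 1 − 0.95^8 = 1 − 0.663 = 33.7%

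**Step 2: false improvements only.** Each two-sided test gives a false improvement with probability 0.025.

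- k = 7: 1 − 0.975^7 = 16.2%
- k = 8: 1 − 0.975^8 = 18.3%

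The comparable rate for a single test is 2.5%.

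**Step 3: correlated tests.** Equally correlated null normal statistics were simulated (400,000 draws per setting), counting draws with at least one |Z| > 1.96, or at least one Z > 1.96 for false improvements. The row for correlation 0 is from the formulas above.

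| Assumed correlation | 7 tests, either direction | 8 tests, either direction | 8 tests, improvement only |
|---|---|---|---|
| 0 | 30.2% | 33.7% | 18.3% |
| 0.3 | 27.2% | 30.0% | 15.2% |
| 0.5 | 23.0% | 25.0% | 12.5% |
| 0.7 | 17.7% | 19.2% | 9.6% |
| 0.8 | 14.8% | 15.8% | 7.9% |

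**Step 4: check with discrete scores.** An illustrative simulation used 50 patients, assumed domain maxima of 5, 3, 6, 3, 2, 5 and 6 points, seven Wilcoxon tests and an exact McNemar test. The either-direction rate for all eight was 31%, 30% and 26% as the assumed within-occasion correlation of the scores rose from 0 to 0.3 to 0.6. The exact McNemar test is conservative here and added only about 1 percentage point to the seven domain tests.

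**Step 5: after adjustment.** The first Holm step for eight tests is 0.05/8 = 0.00625. If all eight nulls are true and the tests are independent, the family-wise rate is 1 − (1 − 0.00625)^8 = 4.9%. In the simulation it was 4.0% at correlation 0.5.

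**The case against.** The strongest reply is that these are labelled secondary analyses in a small single-arm records study with one designated primary test, so the matter is one of reporting. Much of this stands: the primary test is unaffected, which limits the point to secondary claims. But section 8.5 applies a significance rule to all results, and the secondary label does not by itself say that their p-values are descriptive.

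Several stronger readings are tempting and need limiting.

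- **Domains will be wrongly reported as improved a quarter to a third of the time.** The document does not support this. Those rates count both directions, assume no true change in any of the outcomes, and need a correlation of no more than about 0.5. The domains are parts of one scale and the cut-off is on its total, so independence is the least plausible case. If, for illustration, four of the seven domains truly change, the rate among the other three is at most 1 − 0.95^3 = 14% if independent, or 1 − 0.975^3 = 7% for false improvements.
- **The subgroups add a known number of further tests.** Section 8.4 names age, gender and stroke type, subject to sample size, but gives no age categories, test or count. They are already labelled exploratory and enter none of the figures above.
- **The plan was written with the results in view.** The document is dated 2026, the patients were treated in 2018–2019, and section 9 says "Data were collected retrospectively from hospital records". This shows that the data already existed, which the plan largely discloses. It does not show that results had been seen, and it changes no figure here.

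It may also be said that the primary test protects the secondary ones. The plan states no such condition, and a condition alone would not be enough. The domains make up the total, so a real change in one could make the primary significant; the six others, if unchanged, would then carry up to about 1 − 0.95^6 = 26.5% if independent.

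Finally, with no control group (section 4), retest effects or natural recovery could shift scores without any therapy effect. Multiplicity adjustment does not address that. It is a separate limit on what any domain claim can mean.

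**Conclusion.** The concern holds for the secondary claims. Following 8.5 as written, the chance of at least one false-positive result among the eight tests, in either direction, is at most about 34% (30% for the seven domains alone), about 25% at correlation 0.5 and about 19% at 0.7. False improvements are about half of this: about 18% if independent and 13% at 0.5.

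These figures rest on two assumptions: that none of the outcomes truly changes, and a correlation that the document does not give. The rate is lower if some domains truly change. This is a cheap improvement to the plan and not a threat to the primary analysis, but it does alter which domain claims can be made.

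**What to change.** Replace the sentence in 8.5 with:

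> The primary test is at two-sided 0.05. The seven domain tests and the MoCA ≥ 26 test form one secondary family with Holm adjustment at 0.05, tested only if the primary is significant. The Spearman correlation and subgroup results are descriptive, given as estimates with 95% CIs and no significance statement.

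An acceptable and simpler alternative is to report all secondary results as estimates with 95% confidence intervals and make no significance claims for them.

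Either change is SAP wording and needs no new data. Under Holm, the smallest of the eight p-values must be below 0.00625 before any secondary claim can be made, so with 50 patients some single-domain claims may be lost. The alternative avoids that hurdle but gives up all secondary significance claims.
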